- 2. Evaluate whether aspects of the advocacy intervention experience thought to improve outcomes modify the effect of the advocacy intervention on mental health and wellbeing; in particular, to test whether
 - a. the effect changes as the amount of support received increases
 - b. the effect varies according to structural or service characteristics of NGOs;
- 3. Assess the service use and costs associated with advocacy interventions for trafficked people who have been referred into NGO services

8. (a) Study design

Exploratory prospective uncontrolled cohort study and realist evaluation with assessments at baseline (T1) (i.e. at or soon after onset of advocacy support), at 3 months follow up (T2) and at 6-months follow-up (T3). The primary outcome is reduced psychological distress (measured using the CORE-OM) at 3 months follow up (T2) compared with baseline (T1).

(b) Rationale for not including a control group

It is not feasible to recruit a control group for the following reasons: (1) All trafficked people who enter the National Referral Mechanism (NRM) are entitled to government-funded NGO support. Support is provided by a national network of NGOs; there is enough capacity, so NGOs do not operate waiting lists that could serve as a source of controls; (2) Trafficked people who enter the NRM but elect not to receive NGO support are extremely difficult to identify for recruitment. The PI's previous research showed that it is not feasible to recruit from settings such as the NHS and Local Authorities (4).

This study will therefore assess whether mental health among survivors of trafficking improve over the period during which advocacy support is provided, with measures taken at or soon after onset of advocacy intervention, at 3 months follow up, and at after a further 6 months follow up. To support the interpretation of any detected change as a causal intervention effect in the absence of a control group dose-response relationships between change over time and

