Outcomes align with the initial programme theory for the advocacy intervention developed in collaboration with NGOs and informed by relevant literature. Commonly-used, well-validated measures have been chosen where these exist for the outcome of interest and items are relevant to the experiences of trafficking survivors.

Primary outcome

The primary outcome is psychological distress at T2 versus T1. Psychological distress will be measured by the Clinical Outcomes in Routine Evaluation- Outcome Measure (CORE-OM), a 34-item questionnaire which measures global psychological distress. The questionnaire was

designed to assess efficacy and effectiveness across multiple disciplines offering psychological therapies (19). It has good internal and test-retest reliability (0.75-0.95), large differences between clinical and non-clinical samples, and good sensitivity to change (19). Validation work in general population samples shows the CORE-ORM is highly correlated (r=0.77) with the Clinical Interview Schedule-Revised (CISR), supporting convergent validity (20). It has good acceptability in domestic violence research (21, 22) and has been used in research with survivors of human trafficking (23).

Secondary outcomes

Secondary outcomes are CORE-OM score at T3, and health-related quality of life, social support, unmet needs, perceived safety and risk of harm, autonomy, and use of health and social care services at T2 and T3.

- 1. **Health-related quality of life** will be measured using the EQ-5D-5L and SF-12 (25, 26) and the Recovering Quality of Life-10 (ReQoL-10) (27), a new 10-item Patient Reported Outcome Measure (PROM) that has been developed to assess the quality of life for users of mental health services.
- 2. Use of health and social care services will be measured using an adapted version of the Adult Service Use Schedule (AD-SUS) (24). The AD-SUS is a structured instrument which collects data on participants' use of health and social care services for the three-months preceding interview (at baseline) or since the previous interview (at any follow-up point).

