Interviews with staff will explore, for example views about the type of support provided, the ways in which programme components are implemented, the way change is facilitated, current organisational practice and culture, local and national context of trafficking support provision, enabling and constraining factors (contextual factors); what does and does not help survivors and why (mechanisms); and perceived changes in the mental health and wellbeing of service users (outcomes).

13. Participant timeline

The baseline questionnaire (T1) will take place after commencement of individual support planning (i.e. start of intervention) and within two weeks of intake into NGO support services (for clients receiving residential advocacy support) or within 4 weeks of intake (for clients receiving outreach advocacy support).

Follow-up comprises completion of questionnaires at 3 months' follow-up (T2) and at 6 months' follow-up (T3). A 28 day window, defined as 7 days before and 21 days after the due date, will be available to complete the T2 and T3 follow up interviews. Participants who do not complete T2 and T3 interviews with the defined window will be considered to have missed that data collection point. Participants who do not complete T2 interviews will remain eligible to participate at T3.

The data collection timetable is as follows

Research data type	Form name	T1 (Baseli ne)	T2 Follow Up (+90 days)	T3 Follow Up (+180 days)	Ongoing	End of Study
Baseline characteristics	1. Registration Form	X				
Baseline characteristics	2. Eligibility	X				
Baseline characteristics	3. Trafficking-Related Characteristics	X				
Baseline characteristics	5. Immigration and Housing Status	X	X	X		
Primary outcome	6. CORE-OM	X	X	X		
Secondary outcome	7. EQ-5D-5L	X	X	X		
Secondary outcome	8. SF-12	X	X	X		
Secondary outcome	9. ReQoL-10	X	X	X		
Secondary outcome	11. Adapted AD-SUS	X	X	X		
Secondary outcome	12. Adapted PMLDC	X	X	X		
Secondary outcome	13. Adapted SSN	X	X	X		
Secondary outcome	14. Adapted IPV Threat Appraisal and Fear Scale	X	X	X		
Secondary outcome	15. Autonomy	X	X	X		
Process variables	16. Advocacy Support Attendance Log				X	
CONSORT data	4. Status Form		X	X		
CONSORT data	17. Withdrawal Form				X	
-	18. PI Sign Off					X

14. Sample size

Study 1 – Cohort Study

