17. Blinding

There is no blinding of participants, providers, outcome assessors, or analysts.

18. Data collection methods

18a Personnel

To minimise participant burden and facilitate engagement:

- NGO caseworkers will screen incoming clients for eligibility and provide a verbal summary and written information (participant information sheet and consent form) about the study.
- NGO researchers will, after a minimum of 24 hours, confirm eligibility to participate and study information and schedule T1 interview for those intending to participate.
- NGO researchers will take informed consent and administer the T1 questionnaire and T2 questionnaire.

The PI/post-doctoral researcher will visit participating organisations to provide training to NGO researchers to ensure quality and consistency of administration; additional training will be provided as required, for example if new caseworkers are recruited or if problems of questionnaire administration or completion are identified. Fortnightly calls will be made to sites by a post-doctoral researcher to monitor recruitment and completion of questionnaires and enquire about any difficulties with recruitment or administration of questionnaires.

To minimise burden on participating organisations:

- The KCL researcher will administer T3 questionnaires
- The KCL researcher will administer T2 questionnaires to participants who leave the recruiting organisation, e.g. because they voluntarily withdraw from NRM support, because NRM support is withdrawn following a negative reasonable or conclusive grounds decision, or because they are moved to a new NRM support service.
- The KCL researcher will conduct interviews with survivors and staff for the qualitative study.
- Data entry for the cohort study will be completed at KCL under the supervision of the post-doctoral researcher.

To facilitate participation by clients who do are not proficient in English:

• Independent and professionally qualified interpreters will be available to interpret during the provision of information about the study, informed consent processes, and questionnaire administration.

18b Mode

Interviews may be scheduled to take place either face-to-face or by telephone; the mode of interview will be recorded.

18c Interpretation

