Audio recordings of the qualitative interviews will be taken on encrypted digital recorders. Recordings will be transferred onto the secure internal university network with password-protected permissions. Audio files will then be removed from the recording device. Audio files will then be securely transferred to a professional transcription agency following signature of a confidentiality agreement. Transcripts will be downloaded to the secure internal university network and checked against the audio file: after checking, the audio file will be deleted from the university network/server. Transcripts will be anonymised during this checking process.

As per funder guidance, research data will be stored for 10 years after project completion.

19c Data access

Access to participants' personal data will be restricted to the study team (including NGO researchers, for the purposes of data collection and transfer, and Clinical Trials Unit staff), interpreters, transcribers, and auditors. The only exception to that is if a participant discloses something that leads the research team to believe that the participant or another person is at serious risk of harm. In this scenario, the researcher will explain to the participant that they need to break confidentiality to respond to the identified risk. This is detailed on the participant information sheet.

A confidentiality agreement will be in place with transcribers and interpreters.

20. Statistical methods

20a Statistical methods for analysing primary and secondary outcomes

To assess whether receipt of advocacy support is associated with improved mental health a paired samples t-test (or nonparametric equivalent) to assess mean change over the study period (6 months) will be conducted.

20b Methods for additional analyses

To assess whether change over times varies with intervention characteristics (amount of advocacy support received by study participant RQ2 or NGO service characteristics) change scores will be constructed over the intervention period.

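### Section 20a states only a 6-month paired test, while the declared primary outcome is the 3-month change in CORE-OM

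*Protocol*

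**What the plan says.** **Primary outcome.** Protocol section 12 states: "The primary outcome is psychological distress at T2 versus T1". Section 8(a) says the same and identifies T2 as the 3-month assessment, with CORE-OM as the measure.

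**Secondary outcomes.** Section 12 continues: "Secondary outcomes are CORE-OM score at T3", followed by the other scales at T2 and T3.

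**Analysis.** Section 20a covers both the primary and the secondary outcomes. It specifies one procedure, a "paired samples t-test (or nonparametric equivalent) to assess mean change over the study period (6 months) will be conducted".

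**Timing.** Section 13 puts T2 at 3 months (+90 days) and T3 at 6 months (+180 days). Section 8(b) lists a measure at 3 months "and at after a further 6 months follow up".

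**Power.** Section 14 refers to a two-sided 5% paired t-test at both follow-ups, with d=0.18 at T2 and d=0.20 at T3. It calls 250 the required number of participants, after two successive losses of 25% from 450.

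**Interviewers and blinding.** Under section 18a, NGO researchers administer T1 and T2, while "The KCL researcher will administer T3 questionnaires". Section 17 says that analysts are not blinded.

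**The concern.** The only analysis rule for the main question points at a different time point from the declared primary outcome. A 6-month change measured from baseline is T3 against T1, which section 12 ranks as secondary. The 3-month change, which section 12 ranks as primary, has no test in section 20. A statistician writing the analysis plan from 20a would contradict section 12, and one writing it from section 12 would contradict 20a. This is not detail left for a later document: the protocol fixes a time point, and fixes it inconsistently.

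Two things are at stake. First, in an uncontrolled study with unblinded analysts, fixing the primary time point in advance is one of the few protections against choosing the more favourable comparison, and here the text could be cited for either. Second, the two comparisons differ in quality. The 6-month one has more planned loss, so it leans harder on the missing-at-random assumption behind the multiple imputation in 20c. Its baseline and follow-up interviews are also conducted by different groups of people.

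**Working it through.** **1. The statements side by side**

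| Section | Comparison | Status given |
|---|---|---|
| 8(a) | T2 (3 months) vs T1 | primary |
| 12 | T2 vs T1 | primary |
| 12 | CORE-OM at T3 | secondary |
| 14 | T2 vs T1 and T3 vs T1 | both powered, neither ranked |
| 20a | 6 months, i.e. T3 vs T1 | the only test stated; not ranked |

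Section 20b does not settle the matter. It builds change scores over an intervention period to which it gives no length.

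**2. Pairs expected at each time point** (450 recruited, 25% loss, then a further 25%; section 14)

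- T2: 450 × 0.75 = 337.5, about 337 pairs; loss 25%.
- T3: 337.5 × 0.75 = 253.1, about 253 pairs; loss 1 − 0.75² = 1 − 0.5625 = 43.75%, about 44%.
- Check on the target: 250 / 0.5625 = 444.4, so 445 recruits are needed and 450 covers this. The required 250 is therefore the T3 count.

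**3. The protocol's power figures reproduced**

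For a two-sided 5% paired t-test, power = P(T > t₀.₉₇₅,ₙ₋₁), where T is noncentral t with n − 1 degrees of freedom and noncentrality d√n. The opposite tail is negligible.

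- T2, n=337, d=0.18: noncentrality 0.18 × √337 = 3.30; power 90.9%.
- T3, n=253, d=0.20: noncentrality 0.20 × √253 = 3.18; power 88.7%.
- Effect detectable with 90% power: d=0.177 at n=337 and d=0.205 at n=253. These round to the stated 0.18 and 0.20.
- Raw differences with SD 18: 0.18 × 18 = 3.24 and 0.20 × 18 = 3.6, matching the stated 3.2 and 3.6.

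The sample size section is sound for both time points. The T3 figure falls slightly short of 90% because d was rounded down to 0.20.

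**4. Does naming T2 as primary need more participants?**

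A 90% powered test at d=0.18 needs 327 pairs. About 337 are expected, so it does not.

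**The case against.** The best defence is that the intent can be recovered. Sections 8(a) and 12 agree on T2, section 14 names the paired t-test, its sidedness and its level for T2 as well as T3, and 20a never calls the 6-month test primary. That stands, and it rules out two stronger statements: that the protocol nowhere mentions a T2 test, and that it presents a secondary outcome as its main result. It does not repair 20a, because a power statement is not an analysis rule and the section that should carry the rule names only the other time point.

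Other stronger readings a reader might infer also fail:

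- **A large loss of power.** With d=0.18 at T3 (n=253) power would be 81.4%, but that carries the T2 effect size over to T3. The protocol plans d=0.20 there, which gives 88.7%.
- **Type I error of 9.75%.** Two candidate tests would give 1 − 0.95² = 9.75% only if they were independent. These share the T1 score and many of the same people, so the figure lies somewhere between 5% and 9.75%, and the protocol gives no correlation from which to compute it. The study also calls itself exploratory.
- **Interviewer change as a T3-only problem.** Section 18a also has the KCL researcher conduct T2 interviews with people who have left the recruiting organisation. A T2 analysis reduces the problem without removing it.
- **A 9-month final assessment.** The phrase in 8(b) is garbled, and sections 8(a), 13 and 14 all put T3 at 6 months. It is a wording slip.

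It is also fair to note that 20c plans multiple imputation for missing CORE-OM scores and that section 13 lets people who miss T2 return at T3. The planned losses are therefore not simply ignored.

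**Conclusion.** The concern holds as an internal contradiction about the time point of the main analysis. Section 20a specifies the T1 to T3 comparison; sections 8(a) and 12 make T1 to T2 primary. Followed literally, 20a analyses about 253 rather than 337 pairs, with about 44% rather than 25% planned loss and with T3 interviews conducted entirely by a different group from T1, and it leaves the declared primary change without a test in the analysis section.

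The counts rest on the protocol's own attrition assumptions. The power figures treat d as the mean change divided by the standard deviation of the change, as a paired t-test requires. The finding does not extend to the sample size, which supports both time points nearly as stated, and no specific inflation of the error rate can be claimed. Because it concerns which comparison is primary, it should be settled before outcome data are analysed.

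**What to change.** In section 20a, write: *The primary analysis is the mean CORE-OM change from T1 to T2 (3 months); the change from T1 to T3 (6 months) is secondary.*

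In section 8(b), as a wording correction, reword the description of the last assessment so that it agrees with T3 at 6 months (+180 days) in section 13.

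The cost is two sentences. Recruitment, visits, questionnaires and the type of test all stay as they are.

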factors describing the intervention experience will be assessed. Such factors are the "dose of support" which will quantify by frequency and duration of support and "intervention characteristics" (while all NGOs provide advocacy-based support, the structural characteristics of services and the relative emphasis placed on components of support provided vary - reports of the National Audit Office and Public Accounts Committee, and conversations with NGOs, indicate considerable variability between services (9, 18).). Participant characteristics that predict outcomes will also be identified and dose-response analyses will be adjusted for their potential confounding effect.

9. Study setting

A total of six of the 12 NGOs providing government-funded advocacy interventions to survivors of trafficking in England have been purposively selected for variation in structural characteristics and service model. Participating organisations are as follows:

- 1. Ashiana
- 2. BAWSO
- 3. Hestia
- 4. Medaille Trust
- 5. Migrant Help UK
- 6. Salvation Army Accommodation Services

10. Eligibility criteria

Study 1 – Cohort Study

Inclusion criteria

To be eligible for inclusion in the study, participants must meet all inclusion criteria:

- 1. Be aged 18 years or older;
- 2. Have entered into the UK National Referral Mechanism;
- 3. Have consented to receive advocacy support from a participating non-governmental organisation (NGO);
- 4. At date of baseline interview, have received fewer than 14 days' residential advocacy support or 28 days' outreach advocacy support from any NGO through the UK National Referral Mechanism;
- 5. No longer be being exploited by their traffickers.

If the participant has undergone an age determination procedure (i.e. is age-disputed), the participant's age as confirmed by the local authority should be used.

Exclusion criteria

People will be excluded from the study if they:

1. Do not have the capacity to provide consent to participate in the studies, including because of learning disability, psychotic illnesses or severe drug or alcohol problems.

Eligibility will be assessed by trained NGO staff members referred hereafter as "NGO Researchers".

Study 2 - Qualitative study

Inclusion criteria

Survivors- To be eligible for inclusion, survivors must meet the inclusion criteria for the above cohort study and additionally have consented to participate in the qualitative study. English language proficiency is not a selection criterion.

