The study will aim to recruit 450 participants. This will allow a loss to follow up of 25% between T1 (baseline) and T2 (3 months follow up) and a further loss to follow up of 25% between T2 and T3 (6 months follow-up) to ensure we achieve our required sample size of 250 participants. Recruiting 5 participants per NGO per month over an 18-month recruitment period will be sufficient to achieve the desired sample size.

This sample size will be sufficient to detect small standardised differences between at or soon after onset of advocacy (T1) and after receiving advocacy support for 3 months and 6 months (d=0.18 and d=0.20 for T2 and T3 respectively) with 90% power using a two-tailed paired samples t-test at the 5% significance level. These are smaller than effect sizes detected in studies of psychological interventions using the CORE-OM as an outcome measure (32) and in trials of interventions for women who have experienced domestic violence (33-35). The sample size will enable the detection of a pre-post difference score as small as 3.2 and 3.6 at T2 and T3, respectively. This is comparable to pre-post difference scores on the CORE-OM detected by trials of an advocacy intervention for female victims of domestic violence (22). It is also smaller than the reliable change index for the CORE-OM (≥5), i.e. there is sufficient power to detect a statistically significant difference in CORE-OM score (36). Calculations are based on a standard deviation estimate for the CORE-OM (SD=18) taken from baseline data for a sample of trafficked women referred for psychological therapy (23).

Study 2- Qualitative study

The study will aim to recruit up to 30 service users who participated in the cohort study (approximately 6 per participating organisation) and 15 staff (approximately 3 per participating organisation). We will recruit a purposive sample aiming to ensure representation from each of the five participating organisations and to maximize variation in characteristics likely to be relevant to outcomes identified in our preliminary theory of change (e.g. social connectedness, unmet needs, mental health and wellbeing). Based on previous research we expect these characteristics will include gender, type of trafficking, and secure versus insecure immigration status. We will similarly recruit a purposive sample of staff, selecting for variation in level, years of experience, and role.

15. Recruitment

Study 1 – Cohort Study

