The "dose of the support received" will be quantified (e.g. duration in terms of session length, frequency, and the period over which sessions are received; structural and service characteristics NGOs) and change scores will be regressed on this dose. Possible confounders of the dose-response relationship will be identified by testing whether any baseline participant characteristics (e.g. gender, immigration status) predict change over time. Any such potential confounders will then be adjusted for in a second step which regresses the change changes on the dose variable and the putative confounders.

These analyses (which do not include a control group) are based on the assumption that a control group would not exhibit any change over the intervention period. In order to assess the

impact of departures from this assumption on the evaluation of the advocacy support intervention sensitivity analyses will be conducted. Literature evidence will be used to generate a possible distribution of mean outcome change in a hypothetical control group of eligible trafficked woman waiting to start the support program (37); and will then include such sensitivity parameters in our analyses models to study their impact on the estimation of the prepost effect.

20c Methods for handling missing data

In the case of missing data in the CORE-OM outcomes, putative baseline confounders, or process variables, multiple imputation (MI) will be used to ensure that the analyses remain valid under an appropriate missing at random assumption. This will enable us to (multiply) impute realistic outcome patterns including allowing for process variables such as discontinuation of advocacy support to drive loss-to follow-up.

21. Economic evaluation

An exploratory analysis of service use, costs and effects before and after intervention will be undertaken with the results presented using a cost consequences framework, which is recommended for the evaluation of complex interventions that have multiple effects (38). This work will be used to support the generation of recommendations for future research and the development and testing of economic measures appropriate for this population. Specific objectives will include the following:

- 1. Calculate the cost of the advocacy interventions taking a micro-costing (bottom-up) approach (38).

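### Section 20b regresses participants' change scores on NGO characteristics that take only six values, with no NGO-level error term, so standard errors for objective 2b are too small if NGOs differ for other reasons

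*Protocol*

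**What the plan says.** Objective 2 in section 7 is worded as a test, and part (b) asks whether "the effect varies according to structural or service characteristics of NGOs". Section 9 fixes the number of units: "A total of six of the 12 NGOs providing government-funded advocacy interventions to survivors of trafficking in England have been purposively selected", chosen so that structure and service model would vary.

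Section 20b gives the method. For both the amount of support and the NGO characteristics, "change scores will be constructed over the intervention period". Its list of what makes up the dose includes the NGO features: "structural and service characteristics NGOs) and change scores will be regressed on this dose". Baseline participant characteristics that predict change are then identified, and: "Any such potential confounders will then be adjusted for in a second step which regresses the change changes on the dose variable and the putative" (that is, the characteristics so identified). The candidate confounders listed in section 12 are all participant-level (for example gender, age, immigration status and type of exploitation). The protocol does not mention an NGO term, clustering, an ICC or the six-unit limit.

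Section 8(b) gives these analyses weight. Because there is no control group, dose-response relationships, including those with intervention characteristics, are to support a causal reading of the pre-post change. The same section says that outside reports and conversations with NGOs "indicate considerable variability between services".

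**The concern.** A structural or service characteristic is a property of the organisation. Recruiting more clients at the same six NGOs makes each NGO's mean change more precise, but it adds no new values of the characteristic. A regression with one row per participant and no NGO-level error term takes its standard error from the spread between participants. Any difference between NGOs that is unrelated to the characteristic under study is then credited to that characteristic, with too narrow an interval.

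Section 7 seeks the service configurations that appear most beneficial, and section 8(b) uses these relationships to support a causal interpretation of an uncontrolled comparison. A chance difference between a few NGOs could be read both as evidence for a service model and as evidence that the intervention works. The protocol's own premise that services vary considerably makes it hard to assume that no other between-NGO variation exists.

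**Working it through.** **Inputs.** From section 14: "The study will aim to recruit 450 participants", 25% loss from T1 to T2, a further 25% from T2 to T3, two-sided 5% level, 90% power, SD 18. From section 9: six NGOs. Assumed, because the protocol gives none: the ICC of change scores, taken as 0 to 0.05. Also assumed: equal NGO sizes and a characteristic that splits the NGOs 3 v 3.

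**The plan's own figures.** Expected numbers are 450 × 0.75 = 337.5 at T2 and 450 × 0.75² = 253 at T3. A paired t-test has 90.9% power for d = 0.18 at n = 337 and 88.7% for d = 0.20 at n = 253. The raw differences are 0.18 × 18 = 3.24 and 0.20 × 18 = 3.6. The stated figures reproduce to within 2 points of 90% power. They concern the overall pre-post change; the protocol states no power for objective 2b.

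**Type I error of the single-level regression.** With m participants per NGO, the design effect for an NGO-level covariate is DE = 1 + (m − 1) × ICC. The actual error of a nominal 5% test is 2 × [1 − Φ(1.96/√DE)]. Here m = 337/6 = 56.2 or 253/6 = 42.2.

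| Assumed ICC | DE, n = 337 | Type I error | DE, n = 253 | Type I error |
|---|---|---|---|---|
| 0 | 1.00 | 5% | 1.00 | 5% |
| 0.01 | 1.55 | 11.6% | 1.41 | 9.9% |
| 0.02 | 2.10 | 17.7% | 1.82 | 14.7% |
| 0.05 | 3.76 | 31.2% | 3.06 | 26.2% |

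Worked case: ICC 0.02 at n = 337 gives DE = 1 + 55.2 × 0.02 = 2.10, 1.96/√2.10 = 1.35, and a two-sided tail of 0.177.

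Simulation of 8,000 data sets per setting agrees: 11.6%, 18.0% and 30.4% at n = 337, and 9.6%, 14.9% and 26.8% at n = 253, for ICC 0.01, 0.02 and 0.05. A linear NGO-level score in place of the 3 v 3 split gives similar values. A regression on the six NGO means, with 6 − 2 = 4 residual df, stayed at about 5% in every setting.

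**What six units can detect.** For a 3 v 3 split analysed on NGO means, in SD units, SE = √{[ICC + (1 − ICC)/m] × 2/3}. At n = 337 and ICC 0.01 this is √[(0.01 + 0.99/56.2) × 2/3] = 0.136. With 4 df, the difference detectable with 90% power is 0.48 SD at ICC 0, 0.60 at 0.01, 0.70 at 0.02 and 0.93 at 0.05. The single-level calculation suggests (1.96 + 1.28) × 2/√337 = 0.35 SD.

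If SD 18 is applied to change scores, as section 14 in effect does, the range of 0.60 to 0.93 SD is 0.60 × 18 = 10.8 to 0.93 × 18 = 16.7 points. SD 18 is a baseline figure, so the conversion to points is only indicative.

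**The case against.** The strongest reply is that section 20b names no variance estimator, level of analysis or degrees of freedom. A random intercept or cluster-robust errors would be compatible with its wording, and such detail is often left to an analysis plan, which is not at hand. This stands in part: independence of participants is implied by the regression described, not stated. But the protocol does more than stay silent. It names the outcome, the regressor and the adjustment set, and that set stops at participant level. No later document can supply more than six NGO values.

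The study is also labelled exploratory, the analysis is filed under additional analyses, and no power is claimed for it. That lowers the stakes, but it does not make a standard error on the wrong unit acceptable where the objective is worded as a test.

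Some stronger readings are tempting and not supported:

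- A reader might infer that NGO characteristics and individual dose enter one joint model. Section 20b presents them as alternatives, and the list in question is loosely worded.
- A reader might infer that the dose slope in 2a is confounded by client mix. The documents describe variation in services and in intensity of support, not in clients, and measured participant predictors are to be adjusted for.
- A reader might link this regression to the practical guidance on orienting services. That sentence closes section 22 and concerns the qualitative findings.
- A reader might take six as all the NGOs there are. The network has 12, of which six take part.

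**Conclusion.** The concern holds for objective 2b. Followed as written, the regression gives standard errors that are too small if any between-NGO variation remains beyond the characteristic tested. The size of the inflation rests wholly on the assumed ICC and is nil at zero.

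The sample size is uncertain too, because the intervention period is not tied to T2 or T3: section 8(a) sets the primary comparison at 3 months, whereas section 20a speaks of change over 6 months. Multiple imputation could also bring the analysed set back towards 450. The conclusion is the same in each case.

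The six-unit limit does not depend on the ICC. Even with no clustering, a test on NGO means needs a difference of about half an SD for 90% power. Objective 2b can therefore support description but not a dependable test. For 2a, individual dose is affected only so far as dose itself varies between NGOs, which calls for a sensitivity check and not a different main model. This is a change that should be made; it does not threaten the primary outcome.

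**What to change.** For objective 2b, analyse one characteristic at a time, in one of two ways: regress the six case-mix-adjusted NGO mean changes on it (t on 4 df), or fit a participant-level model with a random NGO intercept and small-sample degrees of freedom. State in section 20b that these comparisons rest on six organisations. Present estimates with intervals as descriptive, and reword objective 2b to match. Say also whether the change score runs to T2 or T3.

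For objective 2a, add a sensitivity analysis with NGO as a fixed effect, so that the dose slope is estimated within NGOs. It should not be required as the main model, because it discards the between-NGO dose information for which the sites were partly chosen. If the two slopes differ, report both.

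The change is to wording and analysis only, with no new data. The cost is wider intervals for NGO characteristics, and weaker support from 2b for the causal argument in section 8(b).
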